### **5.0 Enrollment/Randomization**

Following transplant, prior to the one month post-transplant visit, all eligible subjects will be approached either in the transplant unit in the hospital or at the transplant clinic in the hospital for study participation. A random permuted block design will be used to generate random assignments to the groups. This method will ensure balance across the groups over the course of the study period. The biostatistician at the Center for Outcomes Research in Surgery will prepare the master randomization assignment list. Clinical research coordinator will then administer randomization. Since this is an open label study, care providers will not be blinded to the randomization. We do not believe this will interfere with the results of the study or patient care.

Following enrollment, subjects will be randomized at one month post transplant to reduced dose Tacrolimus plus mycophenolic acid (control group) or to Everolimus plus mycophenolic acid (study group) maintenance immunosuppression.

A previous Phase III study (Baboolal, 2003) showed that the mean creatinine clearance rate – a measure to assess the kidney function post-transplant – in the treatment group (those receiving Sirolimus and a CNI (Cyclosporine or Tacrolimus) with planned withdrawal of the CNI) was 65mL/min (SD=14) and in the control group (those who continued to receiving Sirolimus and a CNI) it was 57mL/min (SD=13). Therefore, using the two independent-groups and two-tail t-tests, we will need to recruit 46 patients in each group. With an attrition rate of 11% (Baboolal, 2003), we approximately need 104 participants in this study (52 subjects in each arm) to achieve a statistical power of 80% at 0.05 level of significance. Power analysis and sample size calculation were done using G\*Power 3.1.9.2.

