## **7.0 Data to be Collected**

Target Population: Liver-only transplant patients

Baseline Information: Demographics (age, race, sex, BMI), pre-treatment medical history, pre-treatment concomitant medication.

Intervention: The treatment period starts at 30 days post transplant. Subjects will be followed for up to a total of 36 months post transplant.

During the treatment period relevant concomitant medications, adverse events, complete blood counts, liver function panels, and immunosuppression drug levels will be collected.

Follow-up: Data will be collected at 6 month, 12 month, 24 month, and 36 month timepoints. GFR will be measured at these time points. Any biopsy confirmed rejection that occurs on or before the 36 month timepoint will be recorded. See Table 1 for timeline for data collection.

Occurrence or change in NODAT [New Onset Diabetes mellitus After Transplant], neurocognitive function, hypertension, malignancy, and tolerance will be recorded throughout the length of the study. Results of any ultrasound, ECRP, or biopsy performed for clinical reasons will be recorded throughout the study.

Study follow up will be conducted per standard of care. Patients will not undergo any additional visits for study purposes during treatment or follow up.

Table 1

	days										Months					
	0	1	7	14	21	30 	2 	3 	4 	5 	6 	9 	12 	18 	24 	36 
Sr Creatinine	x	x	x	x	x	x	x	x	x	x	x	x	x	x	x	x
Creatinine Clearance	x	x	x	x	x	x	x	x	x	x	x	x	x	x	x	x
MDRD GFR	x	x	x	x	x	x	x	x	x	x	x	x	x	x	x	x
Sr Glucose	x					x	x	x	x	x	x	x	x	x	x	x
Urine Protein	x					x	x	x	x	x	x	x	x	x	x	x
Lipid profile	x					x	x	x	x	x	x	x	x	x	x	x
BP	x					x	x	x	x	x	x	x	x	x	x	x
LFT	x	x	x	x	x	x	x	x	x	x	x	x	x	x	x	x
Everolimus level							x	x	x	x	x	x	x	x	x	x
Tacrolimus level	x	x	x	x	x	x	#	#	#	#	#	#	#	#	#	#

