## **11.0 Statistical Considerations**

Univariate analysis will be done to describe the distribution of the sample in terms of demographics (age, race, sex, BMI), pre-treatment medical history, pre-treatment concomitant medication. The distribution of the sample will be reported in terms of mean ( $\pm$ SD), median (Inter-quartile range), or percentage depending upon the type of variable (continuous or categorical). Bivariate analysis comparing the sociodemographic variables of the treatment groups will be conducted using chi squared, student T tests, Mann U Whitney, and ANOVA followed by Tukey's pairwise comparison of the means as appropriate.

Intent-to-treat analysis of the data from the baseline and follow-up visits will be analyzed in order to compare the renal functions after liver transplant between the study arm (those receiving Everolimus + mycophenolic acid) and the control arm (those maintained on the low dose Tacrolimus monotherapy + mycophenolic acid therapy). Repeated measures analysis will be conducted to analyze measures of renal function after liver transplant across the treatment groups using multivariable generalized linear model (GLM) over time accounting for the correlation of the measurements obtained for each patient over time. For the secondary end-points, bivariate analysis will be done to compare the outcomes between the treatment and the control groups. Pearson's chi-square, student T tests, and Mann U Whitney tests as appropriate. Adjustment for the correlated variance due to repeated measures will be made throughout the analysis. All analysis will be conducted at 0.05 level of significance using Stata/SE version 14.2 (StataCorp., 2015).

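### Secondary endpoints only: if lipids or urine protein are analysed as continuous values, a comparison adjusted for the day-30 value, with one pre-set contrast, would usually be more precise than the two-sample tests named in Section 11; an optional gain, not a validity error

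*Combined protocol and SAP*

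**What the plan says.** Section 11.0 treats the two groups of outcomes differently. For kidney function, "Repeated measures analysis will be conducted to analyze measures of renal function after liver transplant", using a multivariable generalized linear model that accounts for within-patient correlation. For the rest, "For the secondary end-points, bivariate analysis will be done to compare the outcomes between the treatment and the control groups", and the methods listed are "Pearson's chi-square, student T tests, and Mann U Whitney tests as appropriate". The next sentence adds: "Adjustment for the correlated variance due to repeated measures will be made throughout the analysis". No model, covariate, visit or contrast is named for any secondary endpoint.

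Section 2.0 lists hyperlipidemia and proteinuria among the secondary aims, worded as conditions. Nothing says whether they are analysed as measured values or as yes/no.

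Section 7.0 says "The treatment period starts at 30 days post transplant" and "Data will be collected at 6 month, 12 month, 24 month, and 36 month timepoints". Table 1 schedules the lipid profile and urine protein at day 0, day 30 and months 2, 3, 4, 5, 6, 9, 12, 18, 24 and 36. The day-30 visit has a window of 7 days either side, and Section 6.0 places randomization on post-operative day 30.

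**The concern.** Listing t and Mann-Whitney tests suggests that at least one secondary endpoint may be analysed as a continuous value. Lipids and urine protein are the natural candidates. A two-sample test on a follow-up value makes no use of the pre-treatment value. Nor can it take several values per patient, so it does not by itself deliver the repeated-measures adjustment promised in the same paragraph.

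The stake is precision. With about 46 evaluable patients per arm, an unadjusted comparison may give a wider interval than the collected data allow. A second, smaller matter is that ten post-baseline visits are scheduled and none is named as the one to be compared.

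**Working it through.** **Inputs from the documents.** Significance level: "All analysis will be conducted at 0.05 level of significance" (Section 11.0). Size: "using the two independent-groups and two-tail t-tests, we will need to recruit 46 patients in each group" (Section 5.0), with creatinine clearance means of 65 and 57 mL/min, SDs of 14 and 13, 80% power and 11% attrition. No power is stated for any secondary endpoint, and no correlation between day 30 and follow-up is given.

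**The plan's own figure.** Pooled SD = √((14² + 13²)/2) = 13.51, so d = 8/13.51 = 0.592. A two-sided two-sample t test then needs 46 per arm (power 80.2%; 45 per arm gives 79.3%). With attrition, 46/0.89 = 51.7, so 52 per arm and 104 in total. The figure reproduces. It concerns kidney function and is used here only for the number per arm.

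**Assumptions for the comparison.** Common correlation r between any two visits, equal variance at each visit, complete data. All variances are relative to the unadjusted single-visit t test.

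*One visit.*
- Unadjusted t test: 1.
- t test on change from day 30: 2(1 − r).
- Adjusted for day 30: 1 − r².
- Adjusted against change: (1 − r²)/(2(1 − r)) = (1 + r)/2.

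*Mean of months 6, 12, 24 and 36.*
- Unadjusted: (1 + 3r)/4.
- Adjusted: (1 + 3r)/4 − r².

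| | r = 0.1 | r = 0.3 | r = 0.5 | r = 0.7 |
|---|---|---|---|---|
| One visit: adjusted / unadjusted | 0.99 | 0.91 | 0.75 | 0.51 |
| One visit: adjusted / change score | 0.55 | 0.65 | 0.75 | 0.85 |
| Four-visit mean, unadjusted | 0.325 | 0.475 | 0.625 | 0.775 |
| Four-visit mean, adjusted | 0.315 | 0.385 | 0.375 | 0.285 |
| Four-visit mean: adjusted / unadjusted | 0.97 | 0.81 | 0.60 | 0.37 |

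**Cost of estimating the slope.** With 46 per arm the adjusted variance is multiplied by about 1 + 1/88 = 1.011. At r = 0 adjustment therefore loses about 1%. At r = 0.1 the single-visit ratio is 0.99 × 1.011 = 1.00, which is break-even.

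**Detectable difference.** At one visit with 46 per arm and the slope cost included, the difference detectable with 80% power falls from 0.590 SD (unadjusted t test) to 0.567, 0.514 and 0.424 SD at r = 0.3, 0.5 and 0.7.

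**Simulation check.** With 46 per arm and 4,000 runs per setting, the single-visit variance ratios were 1.02, 0.92, 0.76 and 0.51 at r = 0, 0.3, 0.5 and 0.7. For a 0.5 SD effect at r = 0.5, power was 66% (t test), 64% (Mann-Whitney) and 78% (adjusted). In a separate simulation the type I error of all three methods was 4.8% to 5.3%.

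**If correlation decays.** Let r = c^(months apart/12), with baseline at month 1 and c = 0.3, 0.5 or 0.7. The adjusted/unadjusted ratio is 0.835, 0.687 or 0.479 for the four-visit mean, and 0.890, 0.719 or 0.480 at month 12. At month 36 the gap is 35 months, so r = 0.03, 0.13 or 0.35 and 1 − r² = 0.999, 0.982 or 0.875.

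**The case against.** The strongest reply is that the premise is not established. Every secondary aim is worded as an event or a condition. Section 11.0 uses almost the same list of tests for sociodemographic variables, so the list may be a generic menu. If hyperlipidemia and proteinuria are yes/no per patient, chi-square is suitable and none of the variance figures applies. This stands, and it makes the point conditional.

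Second, the sentence on correlated variance already points towards repeated-measures handling of secondary endpoints. This stands in part. The sentence covers correlation, but it brings in no baseline value, model or contrast.

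Third, a reader might infer that the planned tests discard the day-30 value. The documents do not say so, because they do not state which value per patient enters the test. A t test on change from day 30 is also a two-sample test and does use it. Against that comparator the ratio at r = 0.7 is 0.85, not 0.51. For the four-visit mean the change-score variance is 0.775 + 1 − 1.4 = 0.375, so the ratio is 0.285/0.375 = 0.76, not 0.37.

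Fourth, the change is not entirely free. A model-based mean difference, possibly on a log scale and averaged over 6 to 36 months, estimates something different from a Mann-Whitney comparison. Visits are standard of care only, so day-30 values may be missing, and a plain covariate model would drop those patients. Before month 2, Table 1 has these measurements only at day 0 and day 30. If the day-30 sample falls after randomization, the only scheduled fallback is the transplant-day value, for which the assumed correlations need not hold. All of this stands and shapes the fix.

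**Conclusion.** The point holds as a cheap, optional precision improvement for two secondary endpoints, and only if they are analysed as continuous values. Over an assumed r of 0.3 to 0.7 with complete data, single-visit variance falls to between 0.91 and 0.51 of the unadjusted t test, or to between 0.65 and 0.85 of a change-score t test. Against the unadjusted test the gain vanishes near r = 0.1 and is small at month 36 under decaying correlation.

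Two stronger readings are tempting and are not supported. One is that the named tests are invalid or inflate the error rate: with one value per patient they are valid, and the simulated type I error stays near 5%. The other is that large gains can be counted on: the 0.37 ratio for the four-visit mean needs r = 0.7 held constant to 36 months, complete data and an unadjusted comparator, none of which the documents establish. The primary analysis and the 104 patients are unaffected.

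**What to change.** In Section 11.0:

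- State for each secondary endpoint whether it is continuous or yes/no. Keep chi-square where each patient contributes one yes/no result.
- If lipids or urine protein are continuous, replace the t or Mann-Whitney test with a repeated-measures model of the kind planned for kidney function, adjusted for baseline. Put urine protein on a log or other suitable scale if it is skewed, and state that the estimand then differs from that of Mann-Whitney.
- Fix one between-arm contrast per endpoint in advance: the average over months 6, 12, 24 and 36, or one named visit if a time-specific effect is the question.
- Define baseline as the value from the day-30 window taken on or before randomization. Do not silently substitute the day-0 value. Where the day-30 value is missing or was taken after randomization, keep the patient by modelling baseline as a response with arm means constrained equal, or by another stated method.
- Keep the sentence on correlated variance for any endpoint that uses more than one value per patient.

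The cost is a few sentences and a few more model fits in Stata, which the plan already names. No new data, visits or patients are needed. The statistical price is about 1% of variance if r is 0.

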**Secondary Aims**

Compare the efficacy of Everolimus plus mycophenolic acid versus Tacrolimus plus mycophenolic acid therapy as measured by the following:

- Biopsy-confirmed acute rejection
- Hyperlipidemia
- Proteinuria

- NODAT [New Onset Diabetes mellitus After Transplant], hypertension and malignancy

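### Biopsy-confirmed rejection is compared as a crude proportion although follow-up may be incomplete; cumulative incidence with a month-36 risk difference and 95% interval would serve better

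*Combined protocol and SAP*

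**What the plan says.** All references are to the combined protocol and SAP.

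- **Endpoint.** The Secondary Aims list "Biopsy-confirmed acute rejection" first.
- **Analysis.** Section 11.0 says of all secondary measures: "For the secondary end-points, bivariate analysis will be done to compare the outcomes between the treatment and the control groups". It then names the methods: "Pearson's chi-square, student T tests, and Mann U Whitney tests as appropriate". It names no time-to-event method and plans no confidence interval. The only reporting standard is the 0.05 significance level.
- **Population.** The intent-to-treat sentence in section 11.0 is tied to its stated purpose, "in order to compare the renal functions after liver transplant between the study arm". The sentence on secondary endpoints names no population.
- **Follow-up.** Section 7.0: "Subjects will be followed for up to a total of 36 months post transplant". Section 10.0 lets patients leave, or the investigator withdraw them, at any time.
- **Expected loss.** Section 5.0 inflates the sample size "With an attrition rate of 11"%, from 46 to 52 per arm.
- **Recording.** Section 7.0: "Any biopsy confirmed rejection that occurs on or before the 36 month timepoint will be recorded". The same section says: "The treatment period starts at 30 days post transplant".

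**The concern.** Rejection can occur at any time over roughly three years, and some patients may not be observed for all of it. A chi-square test needs a yes or no for every patient. Someone who leaves at month 10 without rejection must either be scored as a non-event for 36 months or be dropped. The first choice pulls that arm's risk down and the second pushes it up. Section 11.0 does not say which applies, and neither uses the follow-up the patient actually gave.

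If loss is similar in the two arms, the effect on the comparison is modest. If loss differs, the observed difference shifts, and the direction depends on which arm loses more and which rule is used. Unequal loss is possible here because the trial is open-label and withdrawal can be at the investigator's discretion.

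A separate point is what the reader learns from the result. Section 2.0 describes the efficacy and safety of reduced-dose everolimus in preventing rejection as not known. The trial was sized on renal function, so a non-significant chi-square for rejection is likely to be read as reassurance unless the range of compatible differences is shown beside it.

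**Working it through.** **1. The plan's own figure.** Section 5.0 gives means of 65 (SD 14) and 57 (SD 13) mL/min. The pooled SD is sqrt((14² + 13²)/2) = 13.51, so d = 8/13.51 = 0.592. A two-sided t-test at 0.05 has 79.3% power with 45 per arm and 80.2% with 46. Allowing for 11% loss, 46/0.89 = 51.7, which rounds up to 52 per arm and 104 in total. The stated size reproduces. It concerns renal function; the documents give no corresponding figure for rejection.

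**2. Assumptions for rejection.** The documents give no rejection rates and no loss by arm. I assume 36-month risks p = 0.10 (control) and 0.20 (study), a true difference of 10.0 points. Rejection and loss have constant, independent hazards over the T = 35 months between randomisation and month 36. Rejection after a patient leaves is not seen.

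- Rejection hazard: l = -ln(1 - p)/T, which is 0.003010 (control) and 0.006376 (study) per month.
- Loss hazard: c = -ln(1 - d)/T. For d = 0.11, c = 0.003330.
- Leavers kept as non-events: E = [l/(l + c)] × (1 - exp(-(l + c)T)).
- Leavers without rejection excluded: E/(E + C), where C = exp(-(l + c)T) = (1 - p)(1 - d).

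**3. Equal loss of 11%.**

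- Control: E = 0.0945 and C = 0.90 × 0.89 = 0.801. Excluding leavers gives 0.0945/0.8955 = 0.1055.
- Study: E = 0.1892 and C = 0.80 × 0.89 = 0.712. Excluding leavers gives 0.1892/0.9012 = 0.2099.
- Difference: 0.1892 - 0.0945 = 9.5 points (kept), or 0.2099 - 0.1055 = 10.4 points (excluded).

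**4. Unequal loss (illustrative; the same 11% on average).**

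| Loss, control / study | Leavers kept | Leavers excluded |
|---|---|---|
| 11% / 11% | 9.5 points | 10.4 points |
| 5% / 17% | 18.3% - 9.8% = 8.6 points | 21.6% - 10.2% = 11.4 points |
| 17% / 5% | 19.5% - 9.1% = 10.4 points | 20.4% - 10.9% = 9.5 points |

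Differences are taken before rounding. Under these assumptions, cumulative incidence with censoring at loss targets the 10.0-point difference in every row.

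**5. What a p-value leaves out.** These are hypothetical counts out of 52 per arm, with the uncorrected chi-square and the Newcombe 95% interval.

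- 5/52 against 5/52: p = 1.0. The Wilson limits for 5/52 (9.6%) are 4.2% and 20.6%. The half-width for the difference is sqrt((0.0962 - 0.0418)² + (0.2061 - 0.0962)²) = 0.123, so the interval is -12.3 to +12.3 points. The upper limit exceeds the control risk of 9.6%, so a doubling is not excluded.
- 10/52 against 5/52: p = 0.16, difference 9.6 points, interval -4.2 to +23.4.

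**The case against.** The strongest reply is that little hangs on this. Three parts of it stand.

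- **Size.** At the only loss rate in the documents, applied equally, the two rules differ by less than one point (9.5 against 10.4). Every larger figure needs a split between arms that no section supports.
- **The 11% is not a rejection-ascertainment rate.** It was borrowed from a cited study to inflate a creatinine-clearance sample size. Under section 10.0, data collection stops only if consent for disclosure is withdrawn as well, and section 12.0 draws on medical records and third-party requests. A reader might infer that rejection data end at withdrawal; the documents do not say that, and actual loss for this endpoint could be below 11%.
- **The missing interval is general.** Section 11.0 plans none for any endpoint, and naming a test does not prevent an interval from being reported.

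The reply does not remove the point. Follow-up can still be incomplete through withdrawn consent or records that cannot be obtained, and a crude proportion cannot handle that under either denominator. The closing sentence of section 11.0 about correlated repeated measures does not help, because it does not concern a first event per patient under unequal follow-up. Extending intent-to-treat to rejection would settle whom to analyse and in which arm, but not how to score someone last seen at month 10.

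**Conclusion.** This is a minor, inexpensive improvement to a secondary analysis; the documents do not show that the conclusion would be wrong without it. On assumed risks of 10% and 20%, the crude comparison moves a 10.0-point difference to 9.5 or 10.4 at equal 11% loss, and to 8.6 or 11.4 at an illustrative 5%/17% split. These figures rest on constant hazards and on loss unrelated to rejection. The interval is at least as strong a reason for the change: equal counts of 5/52 leave ±12.3 points open.

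Three stronger readings are tempting but unsupported.

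- **Rejections before randomisation dilute the comparison.** Section 7.0 gives an end to recording and no explicit start. However, the sentence sits under follow-up, after a treatment period that begins at day 30, so the natural reading is post-randomisation. Stating the start is a clarification.
- **The denominator choice could distort the result badly.** That needs extreme imbalance, such as loss in one arm only, for which the documents give no basis.
- **The plan mishandles death.** Overstating risk by censoring deaths is a fault of a naive time-to-event analysis, which section 11.0 does not propose. If follow-up were otherwise complete, a crude proportion of all randomised patients with deaths as non-events would equal the competing-risk cumulative incidence.

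**What to change.** In section 11.0, give rejection its own sentence in place of the chi-square. It should specify:

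- the cumulative incidence of first biopsy-confirmed rejection, counted from randomisation and compared by randomised arm;
- censoring at loss to follow-up, with death as a competing event;
- the risk difference at month 36 post transplant, with its 95% confidence interval.

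The sentence also settles the start of the window. Censoring assumes that loss is unrelated to the risk of rejection, so report the number lost and the timing of loss by arm. The same approach could be used for the other new-onset secondary events, NODAT and malignancy.

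The cost is plan wording before analysis. No visits are added: section 7.0 already records rejection to month 36, section 9.0 makes deaths serious adverse events, and section 12.0 makes medical records the primary source. The downsides are slightly more analysis, the need to confirm that dates of rejection, death and last follow-up are captured, and a wide interval that becomes visible.

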## **12.0 Data Management**

Primary Data will be collected directly from the Electronic Medical Record databases CERNER, OTTR, and UNOS. Records requests from third party hospitals will be collected as needed primarily for, but not limited to, Adverse Event reporting and medical history. Adverse Events will be recorded on paper CRFs. Each Adverse Event will be reviewed and attributed by the PI. The Adverse Event CRFs will be signed by the PI. Any lab values, drug levels, or other data not recorded in the Electronic Medical Record will be recorded by study personnel on paper CRFs and signed.

Signed consents and HIPAA authorizations will be stored in study binders. Paper copies of record requests, paper CRFs, and any Notes To File will also be stored in these study

binders. Source material from the Electronic Medical Record will be printed only if needed for data quality control checks and stored in the study binders. Study binders will be stored in a HIPAA compliant, locked room.

Data will be stored electronically in REDCap. The REDCap data file will be backed up manually at least every month on a separate, HIPAA-compliant IU Box Health folder. The database will be built and tested by a biostatistician prior to the production mode.

Data collected in the electronic database will undergo random audits to ensure accuracy. A data safety officer ([name] from Department of Medicine, Division of Nephrology will kindly serve as the data safety officer and will perform quality control checks on the entered data.

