**1.0 Background**

Tacrolimus is the standard immunosuppressive drug used to prevent organ rejection post liver transplant. One side effect of Tacrolimus is nephrotoxicity. Everolimus does not have the nephrotoxicity side effects of Tacrolimus. Replacement of Tacrolimus by Everolimus may have a reduced incidence of renal dysfunction in liver transplant patients who already have chronic kidney disease or peri-operative acute kidney injury. Our liver transplant patients receive potent induction immunosuppression in the form of rabbit anti thymocyte globulin. We believe that in conjunction with this induction regimen, patients can be maintained on Everolimus monotherapy without the risk of rejection. Additionally, Everolimus is known to induce tolerance in transplant recipients. Tolerant patients do not require immunosuppression to accept transplant organs.

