#### Unexpected Adverse Event

An adverse event not mentioned in the package insert or the specificity or severity of which is not consistent with the package insert.

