## Adverse Event (AE) Reporting

Adverse events (AEs) will be reported to the principal investigator immediately and will be recorded from the time of randomization (approximately 30 days after surgery), regardless of whether or not the event(s) are considered related to trial procedures or medications. All AEs considered related to trial medication will be followed until resolution, return to baseline, or deemed clinically insignificant, even if this occurs post-trial.

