### Reporting to the IRB:

1. Unanticipated problems involving risks to subjects or others will be reported **promptly** to the IRB if they:
  1. were unexpected;
  2. were related or possibly related to study participation; AND
  3. suggests that the research places subject(s) or others at greater risk of harm than was previously known.

If the serious adverse event does not meet all three (3) criteria listed above, the event does not have to be promptly reported to the Indiana University IRB.

2. **Prompt** reporting of unanticipated problems to the IRB is defined as within 5 business days of the study team becoming aware of the event.

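### No scheduled, independent by-arm safety review is planned before the final analysis: the data safety officer is assigned only quality control

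*Combined protocol and SAP*

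**What the plan says.** All references are to the combined protocol and SAP.

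- **Data safety officer (12.0).** The one duty stated is that the officer "will perform quality control checks on the entered data".
- **Investigator (9.0 and 12.0).** "Adverse events (AEs) will be reported to the principal investigator immediately and will be recorded from the time of randomization", whether or not they are thought to be related. "Each Adverse Event will be reviewed and attributed by the PI".
- **IRB (9.0).** Prompt reporting needs three things together: the problem is unexpected, it is at least possibly related to participation, and it suggests more risk than was known. "If the serious adverse event does not meet all three (3) criteria listed above, the event does not have to be promptly reported". Unexpected means "An adverse event not mentioned in the package insert or the specificity or severity of which is not consistent with the package insert".
- **Rejection.** "Biopsy-confirmed acute rejection" is a secondary outcome (2.0). "Any biopsy confirmed rejection that occurs on or before the 36 month timepoint will be recorded" (7.0). Section 11.0 compares secondary outcomes between arms with simple two-group tests and describes no interim look.
- **Why rejection matters here.** Section 1.0 states a belief that, after the induction regimen, "patients can be maintained on Everolimus monotherapy without the risk of rejection". Section 2.0 says the efficacy and safety of reduced-dose everolimus in preventing rejection are not known. Under 6.0 the study arm comes off tacrolimus, and those with GFR above 60 at month 3 go on to everolimus alone.
- **Stopping.** Section 10.0 deals with withdrawal of individual subjects only. No monitoring board, periodic by-arm table, review trigger or trial-level stopping provision is described.

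**The concern.** The foreseeable harm of the study strategy is rejection, and the protocol itself says that the question is open. A difference in rejection between arms shows up in counts, not in any single case: each rejection can be a plausible event in a transplant recipient while the tally drifts apart. The plan's oversight steps work mainly on individual events, and the person who attributes them also runs the trial. The officer whose title suggests a safety role has no safety task. If the study arm did have more rejection, the first planned by-arm comparison would be the secondary analysis, and recognising it sooner would depend on the investigator's impression.

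**Working it through.** **1. The plan's own figure.** Section 5.0 gives means of 65 (SD 14) and 57 (SD 13) mL/min, a two-sided 0.05 level, 80% power and 11% attrition.
- Pooled SD = √((14² + 13²)/2) = √182.5 = 13.51; standardised difference = 8/13.51 = 0.592.
- The exact two-sample t-test has power 0.793 at 45 per arm and 0.802 at 46, so 46 is correct.
- 46/(1 − 0.11) = 51.7, rounded up to 52 per arm and 104 in total.

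The stated size reproduces. It was set on renal function and contains no rejection input.

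**2. Who would see a difference in rejection by arm?**

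| Step | What it looks at | By-arm count? | Independent of the investigator? |
|---|---|---|---|
| Investigator (9.0, 12.0) | each event, arm knowable | none planned | no |
| IRB prompt report (9.0) | unexpected, related and greater risk, all three | none planned | yes, but it relies on what is reported |
| Data safety officer (12.0) | accuracy of entered data | none planned | not part of the stated duty |
| Secondary analysis (11.0) | outcomes by arm | yes, with no interim look described | not applicable |

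The definition of unexpected uses mention, specificity and severity. Frequency is not in it, so a higher rate of a listed event does not meet it.

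**3. What one look could do.** The documents give no rejection rates, so the rates below are assumptions. Take one look with 26 per arm (half of 52), all with outcome known, using a one-sided Fisher exact test at 0.05.
- Expected count per arm = 26 × rate.
- Further excess in the next 26 study-arm patients = 26 × (p₁ − p₀). This is an upper bound on what the look could prevent.
- Flag probability = sum of the binomial probabilities of all pairs of counts with p ≤ 0.05.
- Average avoided, if every flag halted enrolment = flag probability × upper bound.

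| Control v study | Expected counts | Flag probability | Upper bound | Average avoided |
|---|---|---|---|---|
| 10% v 10% | 2.6 v 2.6 | 1.6% (false flag) | 0 | 0 |
| 10% v 15% | 2.6 v 3.9 | 7% | 1.3 | 0.1 |
| 10% v 20% | 2.6 v 5.2 | 17% | 2.6 | 0.4 |
| 10% v 30% | 2.6 v 7.8 | 47% | 5.2 | 2.4 |
| 5% v 25% | 1.3 v 6.5 | 55% | 5.2 | 2.8 |

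The last column also assumes that the next 26 study-arm patients are not yet treated at the time of the look. Section 5.0 gives no accrual rate to check this.

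**The case against.** The strongest reply is that the trial is single-center and open label, that every adverse event goes to the investigator at once, and that the investigator signs each one. A reader might infer from the gap that an excess would stay hidden until the end. The documents do not support that: the investigator can know the arm of each reported rejection and may well notice a pattern. This part of the objection stands.

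A reader might also infer that rejection escapes prompt IRB reporting because it is an expected event. That cannot be settled from the text. Being a secondary outcome is not the protocol's test. The test is the package inserts, which are attachments and not reproduced. The third IRB criterion, greater risk than was known, is also not expressly limited to single events. What remains is narrower: a raised frequency of a listed event does not meet the written definition of unexpected, and no one is assigned to produce the count that would reveal it.

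Nor does the plan simply assume safety. The sentence in 1.0 concerns everolimus monotherapy after induction, 2.0 leaves the matter open, and patient-level safeguards exist: exclusion of higher-risk recipients (4.0), serial liver panels and drug levels with biopsy as needed (6.0), and withdrawal of individuals (10.0). These protect the single patient. They do not compare the arms.

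Finally, the data may not be ready to tabulate. Section 12.0 puts adverse events on paper forms without stating their entry into REDCap, graft loss is not a listed data item, and the officer comes from nephrology. These points stand and raise the cost a little.

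**Conclusion.** The point holds in this form: before the final analysis the plan contains no scheduled, aggregate by-arm safety review by anyone independent of the investigator, and the named data safety officer is assigned quality control only. Informal recognition by the investigator is possible, but it is not a substitute for a scheduled count read by someone else.

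The size is modest and conditional. Under assumed rates of 10% versus 30%, one look at 26 per arm flags the difference a little under half the time; under 10% versus 20%, about one time in six. A reader might take 26 × 0.20 = 5.2 as the number of rejections that a look would prevent. It is an upper bound that requires certain detection and an immediate halt with half of the study arm still untreated. With the calculated flag probability the average is about 2.4, and 0.4 for the smaller difference. Limited sensitivity at one look argues for repeated review with judgement, not for a single test. This is a design improvement worth making, not an error in the analysis, and the renal comparison is unaffected.

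**What to change.** In section 12.0, extend the existing data safety officer's task. At fixed intervals (for example every 6 months) the biostatistician supplies a one-page table by arm with the number randomised, follow-up time, and counts since randomisation of biopsy-confirmed rejection, death, graft loss and serious adverse events. The officer's written opinion goes to the investigator and the IRB. State that GFR is not shown by arm, so the 0.05 level for the primary comparison needs no adjustment. Any action rule is for the investigators to set. They should also decide whether the officer needs advice on liver rejection from someone outside the study team.

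Two supporting edits are needed: state in 12.0 that adverse event forms are entered into REDCap, and add graft loss to the data listed in 7.0.

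The cost is a small recurring workload for the biostatistician and the officer, plus that data entry. No extra visits or procedures are required.
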